7.1.5.1. Statistical Methodology Specification

Primary Statistical Analysis
Endpoint / Variables

 Proportion of participants with plasma HIV-RNA greater than or equal to 50 copies/mL at Month 12 (OLI and BIK)/Month 11 (D2I) per Snapshot algorithm for the mITT-E population.
Snapshot Dataset

 Virologic outcome (“HIV-RNA <50” or “≥ 50 c/mL”) per Snapshot algorithm is determined by the last available on-treatment HIV-1 RNA measurement within the analysis visit window of interest (refer to analysis window defined in Section 16.3). In addition, participants who discontinue for reasons not related to adverse event with on-treatment HIV-1 RNA result at the time of discontinuation ≥ 50 c/mL or who change study treatment not permitted per protocol during Maintenance Phase before the analysis visit are classified as ‘HIV-RNA ≥ 50 c/mL’. Full details of the Snapshot algorithm are provided in Appendix 9: Snapshot Algorithm Details
Model Specification

 The primary efficacy endpoint will be analysed using a stratified analysis with Cochran-Mantel-Haenszel (CMH) weights, adjusting for the randomization strata BMI (<30, ≥ 30 kg/m²) and Gender at Birth (female, male)

- The CMH estimate of the adjusted treatment difference will be calculated as a weighted average of strata-specific estimates of the treatment difference calculated within each stratum as follows:
 - Baseline BMI < 30 kg/m² and Male Gender at Birth
 - Baseline BMI < 30 kg/m² and Female Gender at Birth
 - Baseline BMI ≥ 30 kg/m² and Male Gender at Birth
 - Baseline BMI ≥ 30 kg/m² and Female Gender at Birth

- If n_k is the number of CAB LA + RPV LA (Q2M) treated participants, m_k is the number of BIK arm treated participants, and $N_k = n_k + m_k$ is the total number of participants in the k^{th} stratum, then the CMH estimate is given by

$$\hat{d}_{cmh} = \frac{\sum W_k \hat{d}_k}{\sum W_k}$$

where

$$W_k = \frac{n_k m_k}{N_k}$$

are CMH weights and \hat{d}_k are estimates of the differences in proportions between the two treatment arms, p_{Q2M} and p_{BIK} , for the k^{th} stratum.

- The corresponding two-sided 95% CI will be calculated as

$$\hat{d}_{cmh} \pm 1.96 \times \sqrt{\hat{\text{var}}(\hat{d}_{cmh})}$$

where the variance estimator [Sato, 1989] consistent in both sparse data and large strata is given below

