CCI									
CCI									
History of Cosmetic procedures ⁹⁹								X	X

Time and Events Table for BIK to Oral Lead In – Extension Phase:

Procedure	Extension Phase				Withdrawal Assessments ^y	Long-Term Follow-up ^z
	Month					
	13	14	15	Q2M After Month 15		
Eligibility Verification (Inclusion/ Exclusion Criteria)	X ^d					
Symptom Directed Physical Exam and Medical Assessment ^f	X	X	X	X	X	X
Weight, Height and BMIs					X	
Waist Circumference					X	
Hip Circumference					X	
Vital Signs (BP, HR, Temperature) ^h					X	
12-lead ECG ⁱ					X	
HIV Associated Conditions	X	X	X	X	X	X
AEs, SAEs, Concomitant Medications	X	X	X	X	X	X
ISR Assessment for IM injection		X	X	X	X	X
Clinical chemistry and Hematology	X	X	X	X	X	X
Pregnancy Testing ^l	S	U	U	U	S	U
HIV-1 RNA and sample for storage (S) ^m	X	X	X	X	X	X
CD4+ cell count		X	X	X	X	X
CD8+ cell count					X	
Urinalysis ⁿ		X			X	
Fasting Labs Glucose, Cholesterol (Total, HDL and LDL) and Triglycerides ^o		X			X	
Whole Blood (Virology)					X	
CCI						
PBMCs ^q					X	

Procedure	Extension Phase				Withdrawal Assessments ^y	Long-Term Follow-up ^z
	Month					
	13	14	15	Q2M After Month 15		
PK sampling ^u (S)=Storage only		S	S		X	S
Oral CAB and Oral RPV Dispensation ^v	X					
IP accountability (Pill Counts)	X	X				
IM treatment administration ^w		X	X	X		
CCI						

Time and Events Table for BIK to Direct to Injection – Extension Phase:

Procedure	Extension Phase			Withdrawal Assessments ^y	Long-Term Follow-up ^z
	Month				
	13	14	Q2M After Month 14		
Eligibility Verification (Inclusion/ Exclusion Criteria)	X ^d				
Symptom Directed Physical Exam and Medical Assessment ^f	X	X	X	X	X
Weight, Height and BMI ^g				X	
Waist Circumference				X	
Hip Circumference				X	
Vital Signs (BP, HR, Temperature) ^h				X	
12-lead ECG ⁱ				X	
HIV Associated Conditions	X	X	X	X	X
AEs, SAEs, Concomitant Medications	X	X	X	X	X
ISR Assessment for IM injection	X	X	X	X	X
Clinical chemistry and Hematology	X	X	X	X	X
Pregnancy Testing ^j	S	U	U	S	U
HIV-1 RNA and sample for storage (S) ^m	X	X	X	X	X
CD4+ cell count		X	X	X	X
CD8+ cell count				X	
Urinalysis ⁿ		X		X	
Fasting Labs Glucose, Cholesterol (Total, HDL and LDL) and Triglycerides ^o		X		X	
Whole Blood (Virology)				X	
CCI					
PBMCs ^q				X	

Procedure	Extension Phase			Withdrawal Assessments ^y	Long-Term Follow-up ^z
	Month				
	13	14	Q2M After Month 14		
PK sampling ^u (S)=Storage only		S		X	S
IP accountability (Pill Counts)	X				
IM treatment administration ^w	X	X	X		
CCI					

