- f. Physical exams should be conducted as part of normal routine clinical care. Medical assessments include any decisions the study staff must make for participants management and/or care of participant.
- g. Height collected at Baseline Day 1 only. Recommended procedures to measure weight, waist and hip circumference can be found in protocol Section 10.10. Weight related measurements to be collected are weight, body fat %, total body water %, muscle mass, and bone mineral mass.
- h. Measure vital signs after about 5 minutes of rest in a semi-supine position.

- i. A 12-lead ECG will be performed after resting in a semi-supine position for at least 5 minutes. ECGs will be performed pre-dose. ECG pre-dose will be performed in triplicate at Day 1. A 2-hour post-dose ECG will also be performed at Day 1 (D2I), Month 1 (OLI) and Month 12 (OLI)/Month 11 (D2I) for participants receiving CAB LA + RPV LA with an allowable window of ± 30 minutes.
- j. Only SAEs related to study participation or to a concomitantly administered Viiv/GSK product will be collected between obtaining informed consent and administration of study drug at Day 1.
- k. On Day 1, the eC-SSRS is to be administered prior to randomization. The eC-SSRS will be completed at the beginning of the visit following administration of other PROs required prior to injections. The eC-SSRS is not required during the Withdrawal visit if withdrawal occurs during the Extension Phase.
- l. Women of childbearing potential only. S=serum, U=urine. Pregnancy events will be captured starting at Day 1 following initial exposure to study drug. Serum pregnancy test can substitute for urine pregnancy test if locally required but must be appropriately timed to confirm pregnancy status prior to randomization and first IM administration. If the urine test is positive, perform a serum test and do not administer injection. The frequency of pregnancy tests should be performed according to local legal requirements.
- m. Month 12 (OLI and BIK) and Month 11 (D2I) HIV-1 RNA retest (within 4 weeks) for results > 50 c/mL will be captured as unscheduled visit. Plasma for storage samples will be used for possible future analyses.
- n. A morning specimen is preferred. To assess biomarkers: urine albumin/creatinine ratio; urine protein/creatinine ratio; urine phosphate; beta-2-microglobulin; and retinol binding protein.
- o. An overnight fast is preferred; however, a minimum of a 6-hour fast is acceptable.

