16.3.2.3. Assessment Windows for Screening and Maintenance Phase Data –BIK

All Parameters except for where noted ^[a]	Analysis Window	Target Study Day	Analysis Timepoint 1	Analysis Timepoint 2	Notes
	Study Day ≤ 1	Study day of the earliest record	Screening	Screening	
	Last available recorded value up to and including the date of first Maintenance Phase dose of IP	1	Maintenance Baseline (Day 1)	Maintenance Baseline (Day 1)	
post-dose ECG	Value taken post-dose	1	Day 1 (Post Dose)	Day 1(Post Dose)	
	2 ≤ Study Day ≤ 84	57	Month 2	Month 2	
	85 ≤ Study Day ≤ 140	113	Month 4	Month 3/4	
	141 ≤ Study Day ≤ 196				
Urinalysis ^[a] , CD8, CD4/CD8 ratio, fasting glucose and lipids ^[a] , weight, height, BMI, Waist and Hip Circumference, Vital Signs, CCI, Insulin, HbA1c, Renal, Bone and CCI	141 ≤ Study Day ≤ 210	169	Month 6	Month 5/6	
	197 ≤ Study Day ≤ 252	225	Month 8	Month 7/8	
	253 ≤ Study Day ≤ 308	281	Month 10	Month 9/10	
	309 ≤ Study Day ≤ 350				
Urinalysis ^[a] , CD8, CD4/CD8 ratio, fasting glucose and lipids ^[a] , weight, height, BMI, Waist and Hip Circumference, Vital Signs, CCI, Insulin, HbA1c, Renal, Bone and CCI ^[a]	309 ≤ Study Day ≤ 378	337	Month 12	Month 11/12	
	351 ≤ Study Day ≤ Study Day of Last Maintenance BIK Dose +1	365	Month 13	Month 13/14	
If subject permanently discontinued study treatment:					
	Date> (Date of Last BIK Dose +1)		Follow-up	Follow-up	
NOTES:					

 Analysis windows are applied after data has been assigned to the Maintenance Phase as defined in Section 16.4.1 					

- Note for the BIK arm, the “every two months” are implemented as “every 56 days”, therefore the analysis windows are adjusted according to the actual visit schedules instead of nominal.
- Study day is defined in Section 16.6.1
- Follow-up will be derived only for participants who permanently discontinued study treatment.

[a] **Urinalysis:** All parameters provided by the central laboratory under the category of urinalysis.

[b] **Lipids:** Cholesterol, HDL Cholesterol Direct, LDL Cholesterol Calculation, LDL Cholesterol Direct, Total Cholesterol/HDL Cholesterol Ratio, Triglycerides

[c] **Bone Markers:** Bone-specific alkaline phosphatase, Procollagen type 1 N-propeptide, Type 1 collagen cross-linked C-telopeptide, Osteocalcin, 25 hydroxy-Vitamin D; **Renal Markers:** Cystatin C, Retinol Binding Protein, Beta-2-Microglobulin; **CCI**

[d] Analysis windows for parameters with sparse collection are noted.

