CAB LA + RPV LA (OLI)			
Injection Study Day ≤ 15 and Study Day ≥ 2 For those with OLI only: $2 \leq \text{Study Day} \leq 45$	Injection Study Day ≤ 42 and Study Day ≥ 2 For those with OLI only: $2 \leq \text{Study Day} \leq \text{Study Day of Last Oral Dose} + 1$	Month 1	Month 1
$16 \leq \text{Injection Study Day} \leq 60$	$16 \leq \text{Injection Study Day} \leq 72$	Month 2	Month 2
$61 \leq \text{Injection Study Day} \leq 120$	$61 \leq \text{Injection Study Day} \leq 132$	Month 4	Month 3/4
$109 \leq \text{Injection Study Day} \leq 192$	$109 \leq \text{Injection Study Day} \leq 192$	Month 6	Month 5/6
$181 \leq \text{Injection Study Day} \leq 240$	$181 \leq \text{Injection Study Day} \leq 252$	Month 8	Month 7/8
$241 \leq \text{Injection Study Day} \leq 300$	$241 \leq \text{Injection Study Day} \leq 312$	Month 10	Month 9/10
$289 \leq \text{Injection Study Day} \leq 372$	$289 \leq \text{Injection Study Day} \leq 372$	Month 12	Month 11/12
CAB LA + RPV LA (D2I)			
$2 \leq \text{Study Day} \leq 60$	$2 \leq \text{Study Day} \leq 72$	Month 1	Month 1
$61 \leq \text{Study Day} \leq 120$	$61 \leq \text{Study Day} \leq 132$	Month 3	Month 3/4
$109 \leq \text{Study Day} \leq 192$	$109 \leq \text{Study Day} \leq 192$	Month 5	Month 5/6
$181 \leq \text{Study Day} \leq 240$	$181 \leq \text{Study Day} \leq 252$	Month 7	Month 7/8
$241 \leq \text{Study Day} \leq 300$	$241 \leq \text{Study Day} \leq 312$	Month 9	Month 9/10
$289 \leq \text{Study Day} \leq 372$	$289 \leq \text{Study Day} \leq 372$	Month 11	Month 11/12
BIK Arm			
$2 \leq \text{Study Day} \leq 84$	$2 \leq \text{Study Day} \leq 98$	Month 2	Month 2
$85 \leq \text{Study Day} \leq 140$	$85 \leq \text{Study Day} \leq 154$	Month 4	Month 3/4
$127 \leq \text{Study Day} \leq 210$	$127 \leq \text{Study Day} \leq 210$	Month 6	Month 5/6
$197 \leq \text{Study Day} \leq 252$	$197 \leq \text{Study Day} \leq 266$	Month 8	Month 7/8
$253 \leq \text{Study Day} \leq 308$	$253 \leq \text{Study Day} \leq 322$	Month 10	Month 9/10
$295 \leq \text{Study Day} \leq 378$	$295 \leq \text{Study Day} \leq 378$	Month 12	Month 11/12
NOTES:			
○ Apply Snapshot analysis windows only to viral load data that is on-treatment within the Maintenance Phase (See Section 16.4.2).			

- An on-treatment viral load assessment may be assigned to more than one snapshot analysis window.

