Maintenance	
Q2M Arm:
 
For participants continuing into Extension Phase: OLI: Maintenance Treatment Start Date < Date ≤ Date of Nominal Month 14 Injection Visit D2I: Maintenance Treatment Start Date < Date ≤ Date of Nominal Month 13 Injection Visit
 
For participants not continuing into Extension Phase: Maintenance Treatment Start Date < Date ≤ LTFU ART Start Date (if applicable)
 
Note: LTFU ART start date is not applicable for those who complete maintenance phase and transition to commercial supply.

Study Phase	Date range
	
BIK Arm: For participants continuing into Extension Phase: Maintenance Treatment Start Date < Date ≤ min (Start Date of Extension Phase CAB/RPV oral lead-in, Date of first Extension Phase CAB/RPV injection)
 
For participants not continuing into Extension Phase: Date > Maintenance Treatment Start Date

Extension	
Participants continuing maintenance CAB LA + RPV LA into Extension Phase OLI: Date of Nominal Month 14 Injection Visit < Date ≤ LTFU ART Start Date (if applicable) D2I: Date of Nominal Month 13 Injection Visit < Date ≤ LTFU ART Start Date (if applicable)
 
Participants Switching from Maintenance BIK arm to CAB LA + RPV LA: min (Start Date of Extension Phase CAB/RPV oral lead-in, Date of first Extension Phase CAB/RPV injection) < Date ≤ LTFU ART Start Date (if applicable)
 
Note: LTFU ART start date is not applicable for those who transition to commercial supply.

- **Date** = start or assessment date
- **Maintenance Treatment Start Date:** refer to Treatment Start Date in Section 16.6.1

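### In BIK participants who switch, the scheduled Month 13 viral load replaces the Month 12 result in the primary Snapshot outcome; Q2M has no matching scheduled sample in its window.

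*SAP*

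**What the plan says.** The primary endpoint is defined at Month 12 for OLI and BIK and at Month 11 for D2I (SAP 2.4, 7.1.1). Under 7.1.5.1 the Snapshot outcome "is determined by the last available on-treatment HIV-1 RNA measurement within the analysis visit window of interest". Four other parts of the SAP fix what that means in BIK:

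- **Windows (16.3.2.6).** Month 12 for BIK is Study Day 295–378. D2I Month 11 is Study Day 289–372 and OLI Month 12 is Injection Study Day 289–372. The footnote makes the six-week window mandatory at these timepoints. The section adds: "Apply Snapshot analysis windows only to viral load data that is on-treatment within the Maintenance Phase".
- **Phase (16.4.1.2).** For BIK participants entering the Extension, laboratory data are Maintenance when "Maintenance Treatment Start Date < Date ≤ min (Start Date of Extension Phase CAB/RPV oral lead-in, Date of first Extension Phase CAB/RPV injection"). A sample drawn on the day of the first Extension dose is therefore still Maintenance.
- **Treatment state (16.4.3).** The on-treatment upper limit applies only to participants who permanently stop study treatment, so it does not remove a switcher's sample.
- **Schedule (Appendix 2).** Both BIK-to-Extension tables mark HIV-1 RNA at Month 13. Footnote m says, for Month 12 (OLI and BIK) and Month 11 (D2I), that an "HIV-1 RNA retest (within 4 weeks) for results > 50 c/mL will be captured as unscheduled visit".

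The by-visit table for BIK (16.3.2.3) labels Day 351 up to "Study Day of Last Maintenance BIK Dose +1" as Month 13, with target Day 365. Sections 16.3.2.4 and 16.3.2.5 treat the last value up to the first Extension dose as the Extension baseline.

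**The concern.** The endpoint is named for one visit, but the window and last-value rules let a later scheduled visit decide it, in one arm and only for those who switch. BIK non-switchers and all Q2M participants are judged on the Month 12/Month 11 sample or its retest. BIK switchers are judged on Month 13, for which the SAP's retest footnote makes no provision.

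Section 3.2 triggers the primary analysis once the Month 12/Month 11 visits and any retests are complete and does not mention Month 13, so that sample does not appear to have been meant to decide the outcome. None of the sensitivity analyses in 5.5.2 or 7.1.5.1 would reveal its effect. In an open-label non-inferiority trial with a 4-point margin and failure rates likely to be low, one or two reclassified control participants matter. The superiority test that follows uses the same outcome.

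**Working it through.** **1. Reproduce the windows.** The BIK visit interval is 56 days (Appendix 2, footnote b).

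- BIK Month 12 = 1 + 6 × 56 = Day 337. Window 337 − 42 to 337 + 41 = 295 to 378, as stated.
- Q2M target day 331 (16.3.2.1, 16.3.2.2). Window 331 − 42 to 331 + 41 = 289 to 372, as stated.

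**2. Place the next scheduled samples.**

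- BIK Month 13 = 337 + 28 = Day 365, matching 16.3.2.3. This is 378 − 365 = 13 days inside the window.
- Q2M Month 13 (D2I)/Month 14 (OLI) has target day 391. This is 391 − 372 = 19 days outside, and still 12 days outside if the visit is 7 days early.
- Retest within 4 weeks: BIK up to 337 + 28 = Day 365; Q2M up to 331 + 28 = day 359. Both are inside their windows.

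**3. Look for a rule that excludes the Month 13 sample.** The phase rule keeps it, the treatment-state rule keeps it, and 16.3.5 exempts the Snapshot algorithm from the closest-to-target rule. None excludes it.

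**4. Direction.** The last value replaces the Month 12 value; it does not count failure at either visit. Let *f* be the BIK failure rate at Month 12, *s* the switching share, *b* the proportion of suppressed participants newly ≥50 c/mL at Month 13, and *r* the proportion of Month 12 failures re-suppressed by Month 13.

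- Switching requires Month 12 <50 c/mL: rate = *f* + *s·b*(1 − *f*), which can only rise. With *f* = 1%, *s* = 90%, *b* = 0.5%: 0.01 + 0.9 × 0.005 × 0.99 = 1.45%, or 218 × 0.0045 ≈ 1 extra failure. With *b* = 1%: 1.89%, about 2 extra.
- No such requirement: rate = (1 − *s*)*f* + *s*[(1 − *f*)*b* + *f*(1 − *r*)]. With *f* = 1%, *s* = 90%, *r* = 50%, it is 0.55%, 1.0% or 1.44% for *b* = 0, 0.5% or 1%. It can fall, stay or rise.

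**5. Size if the requirement applies.** Inputs from the SAP: about 654 randomised 2:1, so 436 and 218; margin 4 points; two-sided 95% limit. The SAP gives no failure rates or switching share, so those are assumed. The check is an exact binomial enumeration of the event that the upper limit is below 4%, with an unstratified Wald interval standing in for the stratified one. The true Q2M rate is set at the true BIK rate plus 4 points, so every declaration of non-inferiority is false.

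| True BIK rate | Switching | No override | *b* = 0.5% | *b* = 1% |
|---|---|---|---|---|
| 0.5% | 80% | 3.4% | 5.5% | 9.0% |
| 0.5% | 90% | 3.4% | 5.9% | 10.1% |
| 1% | 80% | 2.5% | 4.6% | 7.7% |
| 1% | 90% | 2.5% | 4.9% | 8.7% |

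With both arms truly at 1% and 90% switching, power exceeds 99.9% with or without the override. The upper limit at the expected rates moves from 1.62% to 1.39% (*b* = 0.5%) or 1.14% (*b* = 1%).

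**The case against.** The strongest reply is that this is the declared algorithm working as written. Snapshot takes the last on-treatment value in a six-week window, and Appendix 9's own example lets a Day 350 value override a Day 336 value. Section 16.4.1 deliberately places assessments up to and including the first Extension dose in Maintenance. A pre-dose sample on the switch day reflects BIK exposure, so a raised value there is a genuine on-BIK result. Day 365 is even closer to the OLI Month 12 target (Study Day 361) than Day 337 is, although D2I is assessed at Day 331. All of this is fair. It justifies the phase rule, but not giving one arm a further scheduled sample that overrides the named visit.

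A reader might go further and infer that BIK failures are inflated and non-inferiority is favoured. The document does not support that as a fact. The Extension viral-load criterion is not in the SAP: 2.3 refers only to eligibility requirements, and Appendix 2 (footnote bb) says only that Month 12 data determine them. Nor does the SAP show that a raised Month 13 value would go unconfirmed, since general retest rules may sit in the protocol; only 13 days of window would remain for one. The ±3-day visit allowance is stated for the Maintenance Phase, so the share of switchers sampled by Day 378 is unknown.

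The size also rests on assumptions. Setting *b* at 2% would give error rates of about 17–23%, but that is two to four times the assumed whole-arm failure rate, in people taken to be suppressed four weeks earlier. I do not rely on it.

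**Conclusion.** The mechanism stands on the SAP's text alone: a BIK switcher's Month 12 outcome is the Month 13 value unless that sample is drawn after Day 378, and no scheduled Q2M sample plays the same role. The primary endpoint is therefore read at different visits by arm and, within BIK, by switching status.

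The direction is conditional. If suppression at Month 12 is required to switch, the bias is towards non-inferiority, by about one to two BIK participants in 218 for *b* of 0.5–1%, with false-positive rates of about 4.6–5.9% and 8–10% at a true difference of exactly 4 points. If it is not required, the direction is open. The issue is validity near the margin, not power. It is worth correcting because the rule depends on arm, bears on the primary endpoint and is cheap to remove.

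**What to change.** Leave the phase rule in 16.4.1.2 unchanged. Changing its ≤ to < would move a pre-dose, on-BIK sample into the Extension Phase and could misattribute a BIK rebound in by-phase displays such as Table 2.30.

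Instead, add one line to 16.3.2.6: for the Month 12 Snapshot, BIK viral loads from the nominal Month 13/Extension-baseline visit, including those dated on the day of the first Extension dose, are not used when a Month 12 or Month 12 retest value is available in the window. Identify the sample by nominal visit, because a permitted retest can fall as late as Day 365. For the same reason, do not cap the window at Day 350, which would drop valid retests.

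Report the literal last-value-to-Day-378 version as a named sensitivity analysis. The cost is a small departure from the literal six-week last-value rule and one extra table.

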16.3.2.7. Assessment Windows for Summaries of Long-Term Follow Up Phase Data

Analysis Window	Analysis Timepoint	Target LTFU Study Day of Window
$1 \leq \text{LTFU Study Day} \leq 135$	LTFU Month 3	90
$136 \leq \text{LTFU Study Day} \leq 225$	LTFU Month 6	180
$226 \leq \text{LTFU Study Day} \leq 315$	LTFU Month 9	270
$316 \leq \text{LTFU Study Day} \leq 405$	LTFU Month 12	360
$(30*m - 44) \leq \text{LTFU Study Day} \leq (30*m + 45)$	LTFU Month m m = 15, 18, 21, ...	30*m

NOTES:

- Analysis windows are applied after data has been assigned to the LTFU Phase as defined in Section 16.4.1.
- Long-Term Follow-Up (LTFU) Study day is defined in Section 16.6.1
- An assessment may be slotted to both LTFU and Maintenance/Extension Phase

16.3.3. Assessment Window for Study Conclusion

The study conclusion and Phase conclusion records in disposition data will be slotted based on Section 16.3.1 for Maintenance and Extension Phase conclusion records. However, if the discontinuation date is post-treatment (based on Section 16.4.3), then the discontinuation will be slotted to the participant's last attained on-treatment analysis visit across all assessments (e.g. analysis visit corresponding to the last on-treatment lab assessment), rather than follow up.

16.3.4. Assessment Window for Health Outcome Data

16.3.4.1. HIVTSQs/HIVTSQc/PIN/CCI

Assessments will be assigned to analysis visits as follows:

- Maintenance Baseline (Day 1) will be defined as last available recorded value up to and including the date of first Maintenance Phase dose of study treatment (expected to be collected at Day 1). Baseline is not applicable for PIN, HIVTSQc and other one-time questionnaires such as treatment preference.
- If the nominal visit identifier as captured in the source dataset corresponds to a scheduled collection per the Time and Events Schedule (see Section 16.2) and the assessment is collected in the Maintenance Phase (see Section 16.4.1.2), then the nominal visit identifier will be kept as the analysis visit (excluding Day 1 which will normally be assigned to Maintenance Baseline (Day 1)).
- If the nominal visit identifier is unscheduled or withdrawal, then the following procedure will be used:
 - a. Assign the assessment to a study Phase according to Section 16.4.1.2. Proceed to step b if the assessment is assigned to the Maintenance Phase.

[figure not shown]
- b. Identify the ‘last nominal visit’ with the HO assessment performed prior to the unscheduled/withdrawal visit to be slotted.
- c. Unscheduled/withdrawal visits will be slotted to the planned nominal visit subsequent to the ‘last nominal visit’. If the ‘last nominal visits’ does not exist (e.g. no records originate from a planned nominal visit), then the unscheduled/withdrawal visit will be slotted to the first planned nominal visit after Day 1. If there is already an original (planned) value for the subsequent visit, then the original value will be selected instead of an “unscheduled” value.

Example 1, for HIVTSQs, for Q2M subjects with OLI, the planned nominal visits are Day 1, Month 6, and Month 12. If a participant has the ‘last nominal visit’ (with HIVTSQs assessment) at Month 6 prior to withdrawal at Month 8, the withdrawal assessment will be slotted to the subsequent planned nominal visit of Month 12.

Example 2, for HIVTSQs, for Q2M subjects with OLI if there is unscheduled visit between Month 6 and Month 12, this unscheduled visit will be slotted to Month 12. In this case, there are two assessments with analysis visit equal to Month 12 (i.e. the slotted value and the value at original nominal Month 12 visit). The original nominal value will be selected for summary per the rule below for multiple records—see Section 16.3.5.

Table 6 Planned Nominal Visit of Health Outcome Data

Questionnaire	Day 1	Month 1/2	Month 5/6	Month 11/12
PIN		X	X	X
HIVTSQs	X		X	X
HIVTSQc				X
NOTES: Day 1 visits are recorded as “Baseline” visits in the database.				

